6.3. STUDY PROCEDURE RISKS

There is a very small possibility that misuse of oral hygiene tools could cause gingival trauma, however all participants will receive professional, standardised oral hygiene instructions. Any incidences will be reviewed and treated by dental practitioners.

6.4. PARTICIPANT RECRUITMENT AND SCREENING

Participants will be identified via the following means:

1. Review of existing patient lists. Patients will be screened by LHD staff and if they meet the inclusion criteria will be invited to participate and given a PIS.
2. Advertisements (Poster in a clinic foyer - Level 4 SDH).

Patients attending the clinics at the Sydney Dental Hospital will be invited to participate. BOH, DDS, or Postgraduate Periodontics students providing examinations to patients would assess them for eligibility; provided they met the inclusion and exclusion criteria the patients would then be provided with a Plain Language Statement and Consent form to consider participation.

6.5. PARTICIPANT ENROLMENT

Potential participants will be enrolled into the study after the informed consent process has been completed and the participant has been assessed to meet all the inclusion criteria and none of the exclusion criteria. Study participants will receive a study enrolment number, and this will be documented in the participant's medical (or personal) record and on all study documents.

6.6. INFORMATION AND CONSENT

Potential participants would be provided with a Plain Language Statement and Consent form to consider participation following the screening process. The enrolment visit would be scheduled at least 2 weeks after the screening to allow the patients time to consider the Plain Language Statement and ask any questions.

6.7. RANDOMISATION PROCEDURE

The participant will be randomised at Study Visit 1, after the collection of baseline data and professional plaque removal. A project assistant would provide a randomized allocation (using randomized envelopes) to either the interdental brush or oral irrigation device.

6.8. END OF STUDY TREATMENT/WITHDRAWAL PROCEDURE

A participant can leave the research study at any time. When withdrawing from the study, the participant should let the research team know that they wish to withdraw, either in person, by phone or by email. A participant may provide the research team with the reason(s) for leaving the study but is not required to provide their reason.

The final visit is complete with a final plaque removal, and instructions for routine regular care.

6.9. PATIENT WITHDRAWAL

Participants are free to withdraw from the study at any stage.

7. OUTCOMES

7.1. DEFINITION OF OUTCOMES

Periodontal screening and recording (PSR)

Divide the mouth into sextants. Using a periodontal probe, check six sites on each tooth, but the worst finding in the sextant determines the code.

Code definitions (Landry & Jean, 2002)

Code 0 Absence of clinical signs

Code 1 Bleeding on probing

Code 2 Supra and/or subgingival calculus and/or defective margins

Code 3 Periodontal pocket 4mm to 5.5 mm deep

Code 4 Periodontal pocket 6mm deep

Modified papilla bleeding index

Barnett et al. (1980) modified the PBI index (Muhlemann, 1977) by stipulating that the periodontal probe should be gently placed in the gingival sulcus at the mesial line angle of the tooth surface to be examined and carefully swept forward into the mesial papilla. They timed the appearance of bleeding and graded it as follows:

0 = no bleeding within 30 s of probing;

1 = bleeding between 3 and 30 s of probing;

[figure not shown]
2 = bleeding within 2 s of probing;

3 = bleeding immediately upon probe placement.

The mesial papillae of all teeth present from the second molar to the lateral incisor were assessed. Indices were derived for the maxillary left and mandibular right buccal segments, and the maxillary right and mandibular left lingual segments, and from these a full-mouth index was calculated. This distribution of test sites was utilized since each mesial papilla could only be tested once, i.e. from either the buccal or lingual side. They showed that the modified PBI may be more sensitive than the visual aspects of the GI in assessing changes in gingival health

Rustogi modified navy plaque index

To assess plaque present on teeth, the Modified Navy Plaque Index, developed by Rustogi et al., will be used. Disclosed plaque is scored in each tooth area as present (scored as 1) or absent (scored as 0) and recorded for both buccal and lingual surfaces. Tooth area plaque scores are grouped and designated as Whole mouth = Areas A, B, C, D, E, F, G, H and I, Marginal (gumline) = Areas A, B and C only, Approximal = Areas D and F only.

Patient satisfaction

A short survey to determine participant preference and ease of use for the interdental brushes (Brand: Curaprox) and oral irrigation device (Brand: “Waterpik” Pic Pocket™ subgingival irrigation tip) has been designed by the researchers. It consists of nine short questions.

8. STATISTICAL CONSIDERATIONS

8.1. SAMPLE SIZE OR POWER CALCULATION

40 subjects would be enrolled into the study. A sample size calculation determined 34 participants were required for an effect size of 0.4 (medium sample size approach), with $\alpha=0.05$ and $\beta=0.85$ (G*Power sample calculation software). An additional 20% is included to allow for dropouts.

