Objectives:

Primary objective: To undertake an ethical and independent study to determine whether there is any significant difference in the efficacy of interdental brushes (Brand: “Curaprox” vs Oral Irrigation (Brand: “Waterpik” Pic Pocket TM subgingival irrigation tip) in the removal of plaque and the maintenance of periodontal health.

Secondary objectives: To investigate the patient preference and ease of use for the interdental brushes and Oral Irrigation.

Study design: Within-subjects experimental study design

Planned sample size: 40 subjects would be enrolled into the study.

Selection criteria:

1. Disease status/ or disease group for study: Embrasure space of 2 or 3. PSR code \leq 3.
2. Gender: no restrictions
3. Age range: >18 years
4. At least 24 natural teeth
5. Willingness to provide informed consent and willingness to participate and comply with the study requirements.

Study procedure

Visit 1: Participant enrolment, gain consent; initial full mouth debridement - 2-week break for “Washout”

Visit 2: Clinical parameters would be assessed by clinical examination by two calibrated, blinded examiners (qualified research assistants); dental plaque/stain and supragingival calculus removal; randomised allocation. Participants would use their allocated interproximal aid for 4 weeks.

Visit 3: Clinical parameters will be assessed, and Oral photographs taken. 2-week break for “Washout”.

Visit 4: plaque removed only. Participants would receive OHI and use their allocated interproximal aid for 4 weeks.

Visit 5: Clinical parameters will be assessed, Oral photographs taken; Final AirFlow provided. Participants to complete qualitative satisfaction survey.

Statistical considerations

Sample size calculation: 40 subjects would be enrolled into the study. A sample size calculation determined 34 participants were required for an effect size of 0.4 (medium sample size approach), with $\alpha=0.05$ and $\beta=0.85$ (G*Power sample calculation software). An additional 20% is included to allow for dropouts.

Analysis plan: The analysis will be performed using PRISM (Version 8) statistical software, with the level of significance set at $p<0.05$. The difference in clinical parameters between baseline, and between interventions, will be evaluated using a “Paired t-test”.

Duration of the Study: up to 2 years

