4.2. EXPECTED PARTICIPANT NUMBERS

40 subjects would be enrolled into the study. A sample size calculation determined 34 participants were required for an effect size of 0.5, with $\alpha=0.05$ and $\beta=0.80$. An additional 20% is included to allow for dropouts.

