8.2. PROVIDE A DETAILED ANALYSIS PLAN

The analysis will be performed using PRISM (Version 8) statistical software, with the level of significance set at $p<0.05$. The difference in clinical parameters between baseline, and between interventions, will be evaluated using a “Paired t-test”.

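### The 34 participants said to give 85% power at effect size 0.4 give about 62% for the planned paired t-test, and section 4.2 derives the same 34 from different inputs

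*Protocol*

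**What the plan says.** Protocol section 8.1 states that "34 participants were required for an effect size of 0.4 (medium sample size approach", "with $\alpha=0.05$ and $\beta=0.85$ (G*Power sample calculation software". The statistical considerations in the synopsis give the same inputs and the same result.

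Protocol section 4.2 states instead that "34 participants were required for an effect size of 0.5", with α = 0.05 and β = 0.80.

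All three places enrol 40 ("40 subjects would be enrolled into the study") and explain the margin over 34 in the same way: "An additional 20% is included to allow for dropouts".

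Section 8.2 names one test, a paired t-test, for comparing the interventions. Section 4.1 describes a within-subject design, and the null hypothesis in section 2 has no direction. The protocol gives no sidedness, standard deviation, within-subject correlation or reference outcome for either effect size.

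**The concern.** A smaller effect and a higher power each raise the required sample size. Going from 0.5 at 80% to 0.4 at 85% changes both in that direction, so under one test with one definition of effect size the answer cannot stay at 34. At least one statement is therefore wrong, and the one that turns out wrong is in the synopsis and in the section devoted to sample size.

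This matters most if the trial finds no difference. The primary objective asks whether the two aids differ at all, so a null result is a realistic outcome. A reader who trusts section 8.1 would take it as fairly strong evidence against an effect of 0.4, which the design would quite often miss. The point cannot be left to a later analysis plan, because the protocol itself states the figure.

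**Working it through.** **Inputs.** n = 34, effect size 0.4, α = 0.05, power 85% (synopsis and 8.1). n = 34, effect size 0.5, α = 0.05, power 80% (4.2). Paired t-test (8.2). 40 enrolled, 20% dropout allowance (all three places).

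**Assumptions.** The test is two-sided, as the non-directional hypothesis in section 2 suggests. Effect size is dz, the mean paired difference divided by the SD of the differences. The values labelled β are power; taken literally, β = 0.85 would mean 15% power.

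**Formula.** Power = P(|T| > t with upper tail 0.025 on n − 1 df), where T is noncentral t with n − 1 df and noncentrality dz × √n.

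**Step 1: section 4.2.** dz = 0.5, n = 34: noncentrality 0.5 × √34 = 0.5 × 5.831 = 2.915, power 80.8%. With n = 33 power is 79.5%. The smallest n reaching 80% is therefore 34, and the section 4.2 figure reproduces exactly.

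**Step 2: section 8.1 and synopsis.** dz = 0.4, n = 34: noncentrality 0.4 × 5.831 = 2.332, power 62.0%.

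- Shortfall: 85 − 62.0 = 23.0 points.
- Chance of missing the effect: 100 − 62.0 = 38.0%.
- Smallest n for 85%: 59. Smallest n for 80%: 52.
- Check by normal approximation: ((1.960 + 1.036) / 0.4)² = 56.1, so 57, close to the exact 59.
- Effect detectable with 85% power at n = 34: dz = 0.53.

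**Step 3: power by number of completers.**

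| Completers | dz = 0.4 | dz = 0.5 |
|---|---|---|
| 32 (40 less 20%) | 59.2% | 78.2% |
| 34 | 62.0% | 80.8% |
| 40 (no dropout) | 69.4% | 86.9% |

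**Step 4: dropout.** Adding 20% to 34 gives 34 × 1.2 = 40.8, so 41. Keeping 34 after a 20% loss needs 34 / 0.8 = 42.5, so 43. Enrolling 40 tolerates a loss of 1 − 34/40 = 15%.

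**Step 5: other tests.** Effect size 0.4 and 85% power, two-sided where that applies:

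- Wilcoxon signed-rank: 62.
- Two independent samples: 113 per arm.
- One-way ANOVA, two groups, f = 0.4: 59 in total.
- Correlation of 0.4: 54.
- Repeated-measures ANOVA, two measures, f = 0.4: 31 at within-subject correlation 0, and 17 at 0.5.
- β taken literally (15% power), paired t-test: 8.

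None gives 34.

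**The case against.** The strongest objection is that the protocol never defines its effect size or the sidedness of the test, so section 8.1 might be right on another reading.

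- **Raw effect size.** If 0.4 is the difference over the SD of the raw scores, dz = 0.4 / √(2(1 − ρ)). Reaching dz = 0.53 with n = 34 needs a within-subject correlation ρ of about 0.71. That is possible, but no correlation is stated anywhere.
- **One-sided test.** For dz = 0.4 at 85% this needs 47, and power at 34 is 73.9%, a gap of about 11 points. It also sits badly with section 2, and it would break section 4.2, where 0.5 at 80% would then need only 27.
- **Completers.** If all 40 finish, the two-sided gap at 0.4 is 85 − 69.4, about 16 points.

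So the size of the gap depends on the reading, while the conflict between sections does not. The exact match of section 4.2 favours the two-sided dz reading.

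A second objection is that reproducing arithmetically does not make 0.5 the right target. This stands: the protocol gives no rationale for either value, and 0.4 with 85% appears twice. The correction must not be read as evidence that 0.5 is the difference worth detecting. If the sponsor does want 85% power at 0.4, 40 enrolled is not enough.

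The β label and the shortfall of 40 against 41 are editorial on their own and add no weight to the main point.

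**Conclusion.** The concern holds. The sample-size statement in the synopsis and section 8.1 is wrong for the planned analysis and contradicts section 4.2. With 34 completers, a two-sided paired t-test at 0.05 and 0.4 read as dz, power is about 62% where 85% is claimed; the claim would need 59 completers. The contradiction itself requires only that one test and one definition of effect size apply throughout. The 20% dropout allowance is in effect 15%; a true 20% loss would leave 32 completers, slightly below 80% power even at 0.5. This must be corrected, because the stated power is one the design does not have.

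**What to change.** Use one statement in the synopsis, section 4.2 and section 8.1. The version that reproduces is: 34 completers give 80% power (β = 0.20) to detect a standardised paired difference dz = 0.5 with a two-sided paired t-test at α = 0.05; 40 enrolled allows for 15% dropout.

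If 0.4 is kept as an effect of interest, give its actual power: 62% with 34 completers and 69% with 40. If the figure came from a raw effect size and an assumed correlation, state both so that it can be checked.

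The cost is wording in three places and a less favourable stated power at 0.4. Correcting the statement requires no extra enrolment. Should the sponsor decide that 85% power at 0.4 is truly required, that is a different trial size: 59 completers, or 59 / 0.8 = 73.75, so 74 enrolled with 20% loss.

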8.2. PROVIDE A DETAILED ANALYSIS PLAN

The analysis will be performed using PRISM (Version 8) statistical software, with the level of significance set at $p<0.05$. The difference in clinical parameters between baseline, and between interventions, will be evaluated using a “Paired t-test”.

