4. STUDY DESIGN

4.1. DESIGN

Within-subjects experimental study design

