6. STUDY PROCEDURES

6.1. STUDY FLOW CHART

6.2. INVESTIGATION PLAN

Methodology

Patients attending the clinics at the Sydney Dental Hospital will be invited to participate. BOH, DDS, or Postgraduate Periodontics students providing examinations to patients would assess them for eligibility; provided they met the inclusion and exclusion criteria the patients would then be provided with a Plain Language Statement and Consent form to consider participation. The participants will be given 2 weeks to consider their wish to participate or not and will be asked to call to book in for an appointment to participate in the study should they not wish to consent in writing on the day. A signed consent form will be required prior the participant being admitted into the study.

Visit 1. Is the enrolment visit, study participants would complete their consent form, and will receive a study enrolment number and this will be documented in the participant's medical (or personal) record and on all study documents. Further, they will receive an initial full mouth debridement involving plaque/stain

and gross supra gingival calculus removal using Hand instruments, Ultrasonic instruments and AirFlow (EMS AirFlow) with (PLUS Erythritol powder). There is a 2-week break between Visit 1 and Visit 2.

At **Visit 2**, the following clinical parameters will be assessed:

- Periodontal screening and recording (PSR)
- Modified papilla bleeding index
- Rustogi modified navy plaque index – teeth would be disclosed, and intraoral photos will be taken and assessed later.

Clinical parameters would be assessed by clinical examination by two calibrated, blinded examiners (registered dental practitioners).

Participants will again receive plaque/stain and residual supra gingival calculus removal using Hand instruments, Ultrasonic instruments and AirFlow (EMS AirFlow) with (PLUS Erythritol powder). Project assistants would provide a randomized allocation (using randomized envelopes) to either the interdental brush or water flosser and provide calibrated oral hygiene instructions appropriate to the allocation. Participants would use their allocated interproximal aid for 4 weeks.

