Visit 3, clinical parameters will be assessed. Photographs of their teeth and gums taken to accurately record Modified papilla bleeding index and the Rustogi modified navy plaque index. There will be a “washout” period of 2 weeks when the participants will be asked to return to their normal routine for interdental cleaning, they undertook prior to the study commencing.

Visit 4, the Participants would have all plaque removed only with EMS AirFlow. Again, project assistants would provide calibrated oral hygiene instructions appropriate to the 2nd allocation. Participants would use their allocated interproximal aid for 4 weeks.

Visit 5, clinical parameters will be assessed. Photographs of their teeth and gums taken to accurately record Modified papilla bleeding index and the Rustogi modified navy plaque index, Finally, participants will be asked to complete a anonymous satisfaction survey.

Interventions	Visit 1	Visit 2	Visit 3	Visit 4	Visit 5
Participant Consent	✓				
Inclusion / Exclusion criteria	✓				
Initial full mouth debridement	✓				
Data collection/examination		✓	✓		✓
Plaque removal (airflow)		✓		✓	✓
Blinded allocation		✓			
OHI		✓		✓	
Patient survey					✓
Adverse Event & Serious Adverse Event Assessment					✓

Note: All study procedures are performed as part of routine dental practice.

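### The between-device paired t-test has no period term, although the two crossover periods start after different professional cleaning; a period effect would cost power and, if the sequences are unequal, shift the estimated device difference

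*Protocol*

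**What the plan says.** Section 4.1 describes a "Within-subjects experimental study design". Section 6.2 shows that it is a two-period crossover. The first device is allocated by envelope at Visit 2 and used for four weeks. After a two-week break the participant changes over at Visit 4, when "project assistants would provide calibrated oral hygiene instructions appropriate to the 2nd allocation", and uses the second device for four weeks.

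The two periods begin as follows (section 6.2):

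- **Period 1.** A full-mouth debridement is done at Visit 1. Two weeks later, at Visit 2, "Participants will again receive plaque/stain and residual supra gingival calculus removal using Hand instruments, Ultrasonic instruments and AirFlow".
- **Period 2.** In the two weeks after Visit 3, "the participants will be asked to return to their normal routine for interdental cleaning". At Visit 4, "the Participants would have all plaque removed only with EMS AirFlow".

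The visit schedule shows data collection at Visits 2, 3 and 5, and none at Visit 4.

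On allocation, section 6.7 says "A project assistant would provide a randomized allocation (using randomized envelopes"). It gives no ratio, block size or rule for equal sequences.

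On analysis, section 8.2, which is headed as the detailed plan, says "The difference in clinical parameters between baseline, and between interventions, will be evaluated using a" paired t-test at the 0.05 level. The synopsis repeats this. Period and sequence are not mentioned in either place.

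**The concern.** In a two-period crossover, the brush-minus-irrigator difference within a participant contains the device effect and, with opposite signs in the two sequences, the period effect. A plain paired t-test pools these differences as if they came from one population. The systematic gap between the sequences is counted as noise, and it cancels from the mean only if the sequences are the same size.

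This schedule gives reasons to expect some period effect. Period 1 follows more extensive instrumentation than period 2. By period 2 participants have also had a second round of instruction and some weeks of interdental practice. The outcomes, disclosed plaque and papillary bleeding, could respond to either. With no Visit 4 measurement, a period-specific baseline cannot absorb the effect.

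At stake are the power of the primary device comparison, which has little to spare at 34 completers, and the accuracy of the estimate if the sequences end up unequal.

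**Working it through.** **Inputs from the protocol.** Section 4.2: 34 evaluable participants, effect size 0.5, α = 0.05, and β = 0.80, read as power 0.80. Section 8.2: paired t-test. Sections 4.2 and 8.1: 40 enrolled.

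**Assumed.** The period effect π is not in the protocol. It is set at 0, 0.25 and 0.5 SD of the within-participant difference. Tests are two-sided.

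**Step 1: the protocol's own figure.** For a paired t-test with d = 0.5 and n = 34, the noncentrality is 0.5 × √34 = 2.92 on 33 df, and power is 0.808. This is the smallest n reaching 0.80, so section 4.2 reproduces. (Section 8.1 gives 0.4 and 0.85 for the same n. That does not reproduce, and it is a separate matter.)

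**Step 2: what the paired test estimates.** Let τ be the device difference and π the period 2 minus period 1 effect, with the SD of the difference set to 1. The difference D has mean τ − π in sequence 1 (n1 participants) and τ + π in sequence 2 (n2 participants). Then

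- mean of all D: τ + π(n2 − n1)/n
- variance seen by the paired test: about 1 + 4p(1 − p)π², where p = n1/n.

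At 17/17 and π = 0.5 the variance is 1 + 0.25 = 1.25. At 20/14 the size of the shift is π × 6/34, which is 0.044 SD for π = 0.25 and 0.088 SD for π = 0.5. The latter is 0.088/0.5 = 18% of the target effect.

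**Step 3: the adjusted estimate.** Take the simple average of the two sequence means of D. Here π cancels whatever the split. The standard error is 0.5 × √(1/n1 + 1/n2) on n − 2 df: 0.171 at 17/17, 0.174 at 20/14 and 0.179 at 22/12. Power at τ = 0.5 is 0.81, 0.79 and 0.77, whatever π is.

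**Step 4: rejection rates** (paired test simulated, at least 100,000 trials per setting; true difference 0.5 SD for power). Where two powers are shown, the shift opposes or adds to the effect.

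| Split | π | Shift (SD) | Paired power | Adjusted power | Paired type I error |
|---|---|---|---|---|---|
| 17/17 | 0 | 0 | 0.81 | 0.81 | 0.050 |
| 17/17 | 0.25 | 0 | 0.79 | 0.81 | 0.042 |
| 17/17 | 0.5 | 0 | 0.73 | 0.81 | 0.029 |
| 20/14 | 0 | 0 | 0.81 | 0.79 | 0.049 |
| 20/14 | 0.25 | 0.044 | 0.71 or 0.86 | 0.79 | 0.050 |
| 20/14 | 0.5 | 0.088 | 0.56 or 0.87 | 0.79 | 0.050 |
| 22/12 | 0 | 0 | 0.81 | 0.77 | 0.050 |
| 22/12 | 0.5 | 0.147 | 0.43 or 0.93 | 0.77 | 0.092 |

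The adjusted test holds 0.05 throughout. With simple 1:1 randomisation and π = 0.5, the paired test's type I error averaged over all splits is 0.049.

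**Step 5: how likely is imbalance?** The protocol does not say how the envelopes are generated, so two cases bracket it.

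- Simple 1:1 among 34: 20/14 or worse has probability 2 × P(Binomial(34, 0.5) ≤ 14) = 0.39, and 22/12 or worse has 0.12.
- Envelopes fixed at 20:20 with six participants lost at random: 20/14 needs all six from one sequence, 2 × C(20,6)/C(40,6) = 77,520/3,838,380 = 0.02.

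**The case against.** The strongest defence is that the planned test is valid. Averaged over randomisation the estimate is unbiased and type I error stays near 5%. With equal sequences the test is conservative, and at 20/14 its type I error is still 5%. Inflation to 0.09 needs a 22/12 split and a 0.5 SD period effect together. All of this stands. A reader might infer that the plan raises the false-positive rate; apart from that conditional case, it does not.

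The size is also open. A period effect of 0.5 SD equals the whole device effect used for planning in section 4.2. At 0.25 SD with equal sequences the loss is under 2 points. Both periods begin with plaque removal and device-specific instruction after a two-week interval, and the plaque index scores disclosed plaque. The document therefore supports a plausible period effect, not a certain or large one. A reader might infer that the planned power is lost; that goes beyond what the protocol shows.

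The 0.39 imbalance probability presumes simple randomisation, which is not stated. Silence about blocking is not evidence that there is none.

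Lastly, one might fault the paired test for discarding people who leave after period 1. A two-sample t-test on period differences discards them too; only the mixed model can use their Visit 3 scores.

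These arguments limit the severity. They offer no reason to prefer the unadjusted test, because the stated method omits a term that the design makes relevant and that costs little to include.

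**Conclusion.** The point holds as a should-fix. The protocol itself fixes an analysis that ignores period in a crossover whose periods open after different cleaning. The mechanism is algebraic and applies to any nonzero period effect: extra residual variance always, and a shift of π(n2 − n1)/n in a given trial with unequal sequences.

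The size depends on an assumed π. Over 0 to 0.5 SD, the power lost with equal sequences runs from none to about 8 points (0.81 to 0.73). At 20/14 the shift reaches 0.088 SD, and paired power moves to 0.56 or 0.87 according to direction. These figures also assume 34 completers and a true difference of 0.5 SD. How often imbalance arises (about 0.02 to 0.39 for 20/14 or worse) depends on an envelope procedure that the protocol does not describe. Confidence is high about the omission and modest about its size.

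**What to change.** 1. In section 8.2 and the synopsis, replace the between-device paired t-test with a linear mixed model of the Visit 3 and Visit 5 scores: fixed effects for device, period and sequence, and a random participant effect. For completers, a two-sample t-test comparing period differences between the two sequences is a simple alternative. It is equivalent only with complete data.
2. In section 6.7, state that the envelopes are prepared in permuted blocks giving 20:20 sequences, with the list fixed before any envelope is issued.
3. Do not make the analysis conditional on a preliminary test for carry-over.

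**Cost.** A few sentences of protocol text, a blocked list and one degree of freedom. If there is no period effect, adjustment loses about 1 point of power at 20/14 (0.81 to 0.79 after rounding), 3 to 4 points at 22/12 (0.81 to 0.77), and essentially none at 17/17.

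**Limits.** Period adjustment does not remove carry-over, and it does not supply the missing Visit 4 baseline. Both need their own attention.
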